2. SYNOPSIS

Title of Study:	Safety and Performance of Q-Fix™ All-Suture Anchor System
Study Design:	A retrospective, multi-center, case series
Study Type:	Observational, post-market, clinical follow-up study
Study Product:	Q-Fix™ All-Suture Anchor System Model Specification 72290123 1.8MM MINI 25-1800 1.8MM 25-2800 2.8MM
Study Purpose:	Post-market clinical follow-up needed to address existing clinical data and gaps on the existing Q-Fix™ device and meet existing MDD/MEDDEV requirements
Primary Objective:	To assess the safety and performance data of the Q-Fix™ All-Suture Anchor System.
Statistical Rationale:	The study sample was decided based on the feasibility of recruitment, enrollment and follow-up considerations. Based on the results of a 1.8% failure rate for the Q-Fix™ Suture Anchor in the study conducted by Byrd et al ²⁵ , it is reasonable to estimate a success rate of 95% for the Q-Fix™ Suture Anchors in this study. The proportions of clinical success as defined in this study will be displayed with a confidence interval.
Sample Size:	A total minimum sample size of 90 subjects is proposed with a maximum of 450 subjects (depending on market share) for approved joint indications. Please see table below for enrollment distribution

CONFIDENTIAL AND PROPRIETARY

This document contains information that is confidential and proprietary to Smith & Nephew PLC and Smith & Nephew, Inc. and is intended for use only by Smith & Nephew and its manufacturer. It shall not be reproduced or copied in whole or in part, nor shall the contents be disclosed by any means without prior written permission from Smith & Nephew, nor shall anyone make any use of it that is contrary to the expressed or implied wishes of Smith & Nephew.

Study Protocol—Device	
Safety and Performance of Q-Fix™ All-Suture Anchor System	Number: 17-5010-11
	Version: 2.0 05SEP2019
	Page: Page 5 of 62

	
  
 Joint indication	Number of Subjects	
   
 Hip	Minimum 30 Maximum 150	
 
 Shoulder	Minimum 30 Maximum 150	
 
 Knee	Minimum 30 Maximum 150	
  
	Joint indication	Number of Subjects	Hip	Minimum 30 Maximum 150	Shoulder	Minimum 30 Maximum 150	Knee	Minimum 30 Maximum 150
Joint indication	Number of Subjects								
Hip	Minimum 30 Maximum 150								
Shoulder	Minimum 30 Maximum 150								
Knee	Minimum 30 Maximum 150								
Number of Study Sites:	Approximately 3 sites for each joint indication: up to 9 sites total								
Targeted Global Regions:	United States (US)								
Inclusion Criteria:	
 1. Subject has undergone arthroscopic or open soft tissue repair with Q-Fix™ All-Suture Anchor System 2. Subject was ≥ 13 of age at time of surgery 								
Exclusion Criteria:	
 1. Subject is ≤ 6 months post-operative 2. Subject is entered in another investigational drug, biologic, or device study or has been treated with an investigational product within 12 months post-operative. 								
Study Duration:	
The expected timeline for the study is a total of approximately 2.5 years:
 
 • 6 months for site initiation • 16 months for subject enrollment • 2 months for follow-up • 6 months to analyze the data and prepare the final study report. 								

CONFIDENTIAL AND PROPRIETARY

This document contains information that is confidential and proprietary to Smith & Nephew PLC and Smith & Nephew, Inc. and is intended for use only by Smith & Nephew and its manufacturer. It shall not be reproduced or copied in whole or in part, nor shall the contents be disclosed by any means without prior written permission from Smith & Nephew, nor shall anyone make any use of it that is contrary to the expressed or implied wishes of Smith & Nephew.

Study Protocol—Device	
Safety and Performance of Q-Fix™ All-Suture Anchor System	Number: 17-5010-11
	Version: 2.0 05SEP2019
	Page: Page 6 of 62

Primary endpoint:	
 • Clinical success rate, defined as subjects without re-intervention at 6 months post-operative, as assessed by the surgeon
Secondary endpoints:	
 • Clinical success rate, defined as subjects without re-intervention at 12 months post-operative, as assessed by the surgeon • Visual Analog Scale (VAS) - pain • Range of Motion (ROM) • Clinical success rate in adolescents and young adults, defined as subjects ages 13-21 years of age without re-intervention at 6 and 12 months post-operative
Safety Endpoints:	
 • Device-related re-intervention • All adverse events (AEs) occurring from the time of surgery until revision or study completion • Device related AEs and serious adverse events (SAE's)

CONFIDENTIAL AND PROPRIETARY

3. STUDY SCHEMATIC

Table 1: Schedule of Events

Schedule of Events	Chart Review ^{1,2}		
	Screening	182 days post-op 6M (±91 Days)	365 days post-op 12M (± 91 Days)
Inclusion/Exclusion	X		
Case History Review***	X		
Implant Status ³	X	X	X
VAS	X	X	X
ROM	X	X	X
Concomitant Medications, Procedures ⁴	*	*	*
AE Assessment	*	*	*
Study Implant Disposition	*	*	*
Serious Adverse Event (SAE) / Adverse Device Effect (ADE) / Device Deficiency (DevD) Assessment	*	*	*
End of Study/Subject disposition	*	*	*

¹ Given the retrospective study design, data will be collected to the extent it is available.

² Informed consent/waiver of informed consent from the IRB must be obtained prior to retrospective data collection.

³ Subjects who have undergone a revision procedure of the anchor will be considered terminated from the study from the date of the revision. Study related data will not be collected following the date of the revision.

⁴ Any concomitant medications/ procedures associated with an AE, SAE or SADE will be recorded.

* If applicable

*** Review of subject demographics, medical history, operative, post-operative, discharge, and cumulative AE's occurring since date of surgery

CONFIDENTIAL AND PROPRIETARY

This document contains information that is confidential and proprietary to Smith & Nephew PLC and Smith & Nephew, Inc. and is intended for use only by Smith & Nephew and its manufacturer. It shall not be reproduced or copied in whole or in part, nor shall the contents be disclosed by any means without prior written permission from Smith & Nephew, nor shall anyone make any use of it that is contrary to the expressed or implied wishes of Smith & Nephew.

Study Protocol—Device	
Safety and Performance of Q-Fix™ All-Suture Anchor System	Number: 17-5010-11
	Version: 2.0 05SEP2019
	Page: Page 8 of 62

4.3 LIST OF ABBREVIATIONS

Abbreviation	Definition
ADE	Adverse Device Effect(s)
AE	Adverse Event(s)
AOL	Activities of Daily Living
CRF	Case Report Form(s)
CSR	Clinical study Report
CTA	Clinical Trial Agreement
CV	Curriculum Vitae
DevD	Device Deficiency(ies)
FU	Follow-Up

CONFIDENTIAL AND PROPRIETARY

This document contains information that is confidential and proprietary to Smith & Nephew PLC and Smith & Nephew, Inc. and is intended for use only by Smith & Nephew and its manufacturer. It shall not be reproduced or copied in whole or in part, nor shall the contents be disclosed by any means without prior written permission from Smith & Nephew, nor shall anyone make any use of it that is contrary to the expressed or implied wishes of Smith & Nephew.

Study Protocol—Device	
Safety and Performance of Q-Fix™ All-Suture Anchor System	Number: 17-5010-11
	Version: 2.0 05SEP2019
	Page: Page 11 of 62

Abbreviation	Definition
GCP	Good Clinical Practice
IBT	Iliotibial Band Syndrome
ICF	Informed Consent Form
ICH	International Conference on Harmonisation
ICMJE	International Committee of Medical Journal Editors
IFU	Instructions for Use
IP	Investigational Product
IRB	Institutional Review Board
ISF	Investigator Site File
ISO	International Organization for Standardization
LCL	Lateral Collateral Ligament
MCL	Medial Collateral Ligament
MEDDEV	MasterControl European Medical Device Vigilance System
MDD	Medical Device Directive
NA or N/A	Not Applicable
NSAIDs	Nonsteroidal anti-inflammatory drugs
NSAE	Non-Serious Adverse Event(s)
PI	Principal Investigator
PP	Per-Protocol Population
ROM	Range of Motion
S&N	Smith & Nephew, Inc.
SADE	Serious Adverse Device Effect(s)
SAE	Serious Adverse Event(s)
SAF	Safety population
SAP	Statistical Analysis Plan

CONFIDENTIAL AND PROPRIETARY

This document contains information that is confidential and proprietary to Smith & Nephew PLC and Smith & Nephew, Inc. and is intended for use only by Smith & Nephew and its manufacturer. It shall not be reproduced or copied in whole or in part, nor shall the contents be disclosed by any means without prior written permission from Smith & Nephew, nor shall anyone make any use of it that is contrary to the expressed or implied wishes of Smith & Nephew.

Study Protocol—Device	
Safety and Performance of Q-Fix™ All-Suture Anchor System	Number: 17-5010-11
	Version: 2.0 05SEP2019
	Page: Page 12 of 62

Abbreviation	Definition
SLAP	Superior Labral Tear from Anterior to Posterior
UHMWPE	Ultra-high molecular weight polyethylene
USADE	Unanticipated Serious Adverse Device Effect(s)
VAS	Visual Analog Scale
VMO	Vastus Medialis Obliquus

CONFIDENTIAL AND PROPRIETARY

This document contains information that is confidential and proprietary to Smith & Nephew PLC and Smith & Nephew, Inc. and is intended for use only by Smith & Nephew and its manufacturer. It shall not be reproduced or copied in whole or in part, nor shall the contents be disclosed by any means without prior written permission from Smith & Nephew, nor shall anyone make any use of it that is contrary to the expressed or implied wishes of Smith & Nephew.

Study Protocol—Device	
Safety and Performance of Q-Fix™ All-Suture Anchor System	Number: 17-5010-11
	Version: 2.0 05SEP2019
	Page: Page 13 of 62

5. INTRODUCTION

5.1 BACKGROUND

Bone anchor fixation devices are typically indicated for a variety of repairs in the shoulder, elbow, hand/wrist, hip, knee and foot/ankle. There are numerous alternative therapy options associated with these indications including conservative therapies such as rest, nonsteroidal anti-inflammatory drugs (NSAIDs), injection of steroids with lidocaine, and physical therapy. Several clinical studies were identified that reported higher clinical outcomes, or the ability to return to previous level of activity^{1,2}, or lower complication/reinjury rate^{2,3} in patients that were treated surgically rather than conservatively. When conservative therapy does not offer relief of symptoms for the patient, surgical intervention is often recommended. One method of surgical intervention is to repair using an implant such as an interference screw or suture anchor. Interference screws provide a press fit between bone to bone, or bone to graft/tendon whereas suture anchors approximate soft tissue with an implant embedded in the bone. The use of suture anchors may provide advantages such as reduced operative time, ease of access to the site of implantation, improved suture material, decreased stress along the suture line, greater repair strength, and improved consistency of load-to-failure characteristics⁴⁻⁷. Patient bone density, repair location, potential allergies, the operation being performed and surgeon preference determine the size, type and composition of the anchor needed to secure the soft tissue to the bone⁸.

Non-absorbable, soft suture anchors have recently been introduced for use in arthroscopic or open soft tissue to bone reattachment. Soft suture anchors or all-suture anchors are completely suture-based implants. The anchors usually come with single or double loaded suture options. Soft anchors are usually smaller than hard anchors; hence the volume of bone removed is less, which is especially helpful should subsequent revision be necessary⁹⁻¹⁰. Additionally, the small size enables placement of anchors in very close proximity to each other allowing multiple sutures/fixation points per unit area of soft tissue⁹. The few studies that have investigated all-suture anchor biomechanics, such as cyclic loading and pullout mechanics, suggest that they are comparable to traditional anchors¹⁰⁻¹³. Soft anchors have also been

CONFIDENTIAL AND PROPRIETARY

This document contains information that is confidential and proprietary to Smith & Nephew PLC and Smith & Nephew, Inc. and is intended for use only by Smith & Nephew and its manufacturer. It shall not be reproduced or copied in whole or in part, nor shall the contents be disclosed by any means without prior written permission from Smith & Nephew, nor shall anyone make any use of it that is contrary to the expressed or implied wishes of Smith & Nephew.

Study Protocol—Device	
Safety and Performance of Q-Fix™ All-Suture Anchor System	Number: 17-5010-11
	Version: 2.0 05SEP2019
	Page: Page 14 of 62

reported to provide a comparable, or even higher, mechanical strength than that measured for the interference screw technique¹⁴.

Typically, manufacturers of anchor systems market suture anchors preloaded with suture(s) that the anchor has been designed and tested with; furthermore, the manufacturer’s Instructions for Use (IFU) will specify the type of suture and how many strands may be used with an anchor. Suture anchors are continuously evolving to improve anchor strength and to facilitate arthroscopic or open procedures. Soft suture anchors are the newer anchors on the market that have pursued fixation differently with the all-suture design. The Juggerknot 1.4 was the first all-suture construct that was designed to avoid potential sequelae from the migration and third body wear of a rigid anchor body, to provide radiographic images unobscured by metal hardware, and to facilitate revision procedures. The small 1.4 mm diameter of the drill hole helps to minimize compromise to the bone while allowing for multiple points of soft tissue fixation¹⁵.

Based on the injury type and the anatomical position of the injury, the single- and double-loaded Q-Fix™ Suture Anchor designs offer the surgeon more flexibility when determining the type of repair. The smaller footprint required by these devices allows the placement of multiple implants in a limited area, which promotes greater tissue-to-bone contact.

A summary of known and potential risks and benefits to humans can be found in the IFU.

5.2 STUDY PURPOSE

Post-market clinical follow-up needed to address existing clinical data and gaps on the existing Q-Fix™ device and meet existing MDD/MEDDEV requirements.

CONFIDENTIAL AND PROPRIETARY

This document contains information that is confidential and proprietary to Smith & Nephew PLC and Smith & Nephew, Inc. and is intended for use only by Smith & Nephew and its manufacturer. It shall not be reproduced or copied in whole or in part, nor shall the contents be disclosed by any means without prior written permission from Smith & Nephew, nor shall anyone make any use of it that is contrary to the expressed or implied wishes of Smith & Nephew.

Study Protocol—Device	
Safety and Performance of Q-Fix™ All-Suture Anchor System	Number: 17-5010-11
	Version: 2.0 05SEP2019
	Page: Page 15 of 62

5.3 SAFETY CONSIDERATIONS

The Q-Fix™ All- Suture Anchor System is intended to be used for soft tissue to bone fixation in the Shoulder, Knee, and Hip. Representative language of the contraindications and potential adverse effects from the Q-Fix™ All-Suture Anchor can be found in the Instructions for Use (IFU). Cleaning and Sterilization Language can be found on the Reusable Surgical Instruments IFU.

6. STUDY RELATED RISKS

6.1 STUDY POSSIBLE RISKS

As a result of participating in the study, there could be a risk of loss of protected subject information confidentiality. All applicable confidentiality standards and data protection and privacy laws will be followed by the Sponsor to ensure that data collected is handled in confidence. Data will be coded and handled only by appropriately qualified and authorized personnel.

6.2 STUDY RELATED BENEFITS

Because the surgery and all the follow-up visits are the same as if the subject would not participate in this study, there are no additional medical benefits associated with participating in this study. The information gained from this study may help improve the treatment of people that need to undergo any of the procedures included in this study.

7. OBJECTIVE(S)

7.1 PRIMARY OBJECTIVE

The primary objective of this study is to assess the safety and performance of the Q-Fix™ All-Suture Anchor System.

8.1 IDENTIFICATION

8.1.1 Indications

The Q-Fix™ All-Suture Anchor System is intended to be used for soft tissue to bone fixation for:

- **Shoulder:** Bankart lesion repair; superior labral tear from anterior to posterior(SLAP) lesion repair; acromio-clavicular repair; capsular shift/capsulolabral reconstruction; deltoid repair; rotator cuff repair; biceps tenodesis.
- **Hip:** Acetabular labral repair.
- **Knee:** Extra-capsular repair: medial collateral ligament (MCL), lateral collateral ligament (LCL) and posterior oblique ligament; Iliotibial band tenodesis (IBT); patellar tendon repair; vastus medialis obliquus advancement (VMO); joint capsule closure

Note: Foot, ankle, elbow, hand and wrist indications are not included in the above list as data will not be collected. As the study is collecting real world data retrospectively, data may be collected on the shoulder, knee, or hip beyond the indications listed above.

8.1.2 Device Information

The Q-Fix™ All-Suture Anchor System also known as the Q-Fix™ Soft Suture Anchor System/ Q-Fix™ Soft Suture Anchor/ Q-Fix™ Suture Anchor is available in 1.8 mm (single suture loaded) and 2.8 mm (double suture loaded) sizes; is manufactured from braided polyester with ultra-high molecular weight polyethylene (UHMWPE) suture; and is pre-loaded into a disposable tool designed to facilitate direct insertion into a pre-drilled or pre-punched bone hole. Table 8.1-1 demonstrates the model, specifications, dimensions and product description of the Q-Fix™ All- Suture Anchor System.

The Q-Fix™ MINI Suture Anchor minimizes bone removal by shortening the drill tunnel depth by 5mm. This drill depth of 17.1mm is approximately 23% shorter than the existing Q- Fix™ 1.8mm anchor.

[figure not shown]
[figure not shown]
[figure not shown]
CONFIDENTIAL AND PROPRIETARY

This document contains information that is confidential and proprietary to Smith & Nephew PLC and Smith & Nephew, Inc. and is intended for use only by Smith & Nephew and its manufacturer. It shall not be reproduced or copied in whole or in part, nor shall the contents be disclosed by any means without prior written permission from Smith & Nephew, nor shall anyone make any use of it that is contrary to the expressed or implied wishes of Smith & Nephew.

Study Protocol—Device	
Safety and Performance of Q-Fix™ All-Suture Anchor System	Number: 17-5010-11
	Version: 2.0 05SEP2019
	Page: Page 17 of 62

When the soft suture anchor is deployed into the predrilled/punched hole, the suture legs are tensioned, increasing the soft anchor’s diameter, locking the anchor suture against the cortical bone. The soft suture nature of the anchor allows the suture to be placed in a tunnel with a smaller diameter, preserving more bone.

Table 8.1-1: Product performance, structural composition and specification model of device

Model	72290123	25-1800	25-2800
Specification	1.8 mm MINI	1.8 mm	2.8 mm
Dimensions			
Diagram			
Product description	1.8 mm wide x 10mm long Q-Fix™ MINI All-suture Anchor, single-loaded with a #2 MAGNUMWIRE™ suture	1.8 mm wide x 15mm long Q-Fix™ All-suture Anchor, single-loaded with a #2 MAGNUMWIRE™ suture	2.8 mm wide x 20mm long Q-Fix™ All-suture Anchor, double-loaded with a #2 MAGNUMWIRE™ suture

CONFIDENTIAL AND PROPRIETARY

This document contains information that is confidential and proprietary to Smith & Nephew PLC and Smith & Nephew, Inc. and is intended for use only by Smith & Nephew and its manufacturer. It shall not be reproduced or copied in whole or in part, nor shall the contents be disclosed by any means without prior written permission from Smith & Nephew, nor shall anyone make any use of it that is contrary to the expressed or implied wishes of Smith & Nephew.

Study Protocol—Device	
Safety and Performance of Q-Fix™ All-Suture Anchor System	Number: 17-5010-11
	Version: 2.0 05SEP2019
	Page: Page 18 of 62

Q-Fix™ Soft Suture Anchor Disposable Surgical Instruments and Instrument Kits

The Q-Fix™ Soft Suture Anchor Disposable Surgical Instruments and Instrument Kits contain sterile, single-use disposable devices. The kit includes a drill, a drill guide and an obturator.

Q-Fix™ Soft Suture Anchor Reusable Surgical Instruments

The Pathfinders and Bone Punch devices are manufactured of surgical stainless steel with a part of the device including plastic. The Q-Fix™ Reusable Drill Guides and Obturators are made of surgical stainless steel with Acetal Copolymer handles.

ArthroCare Corporation is a wholly-owned subsidiary of Smith & Nephew, Inc. ArthroCare Corporation is the legal manufacturer of the study devices. Smith & Nephew, Inc. globally distributes the study devices

8.2 PRODUCT USE

Each device is packaged with an IFU (62526.en)²¹ to ensure that the device is used properly and for the intended procedures. For the purposes of this protocol, unless otherwise noted in the operative report, the delivery system for the device worked correctly since the device was deployed.

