9.2 INCLUSION CRITERIA

Subjects will be considered qualified for enrollment if they meet the following criteria:

1. Subject has undergone arthroscopic or open soft tissue repair with Q-Fix™ All-Suture Anchor System
2. Subject was ≥ 13 of age at time of surgery

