11.1.2 Retrospective: Screening

Given the retrospective study design, data will be collected to the extent it is available.

- Obtain informed consent, as required by the IRB, on and IRB approved ICF or a waiver of informed consent as detailed in Section 9.5
- Do not proceed until consent has been obtained -----**
- Screen the subject for protocol inclusion/exclusion criteria.
 - Assign the subject a subject ID
 - Collect the following retrospective data, to the extent is available in the subject’s medical records, per CRF completion guidelines:
 - Case History Review (Review of subject demographics, medical history, operative, post-operative, discharge, and cumulative AE’s occurring since date of surgery)
 - Implant status
 - VAS (pain) – preoperative if available
 - ROM - preoperative if available
 - Implant Status CRF, if applicable
 - Study Implant Disposition CRF, if applicable
 - AE assessments- if applicable
 - Concomitant medications/ procedures associated with an AE, SAE or SADE will be recorded- if applicable
 - End of Study CRF, if applicable

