12.2 ANALYSIS POPULATIONS

The following analysis populations will be used for this study:

- **Safety Population (SAF):** This includes all subjects who enroll in the study who had previously undergone arthroscopic or open soft tissue repair using the Q-Fix™ All-Suture Anchor System i.e. subjects who only provide retrospective data.
- **Per-Protocol Population (PP):** This includes all subjects in the Safety Population, who have no significant protocol deviations and who meet all the inclusion/exclusion criteria.

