12.4 SAFETY ANALYSES

All safety analyses will be conducted using the safety population. The number of incidences and number of subjects reporting all adverse events will be summarized both overall and by seriousness, severity,

CONFIDENTIAL AND PROPRIETARY

This document contains information that is confidential and proprietary to Smith & Nephew PLC and Smith & Nephew, Inc. and is intended for use only by Smith & Nephew and its manufacturer. It shall not be reproduced or copied in whole or in part, nor shall the contents be disclosed by any means without prior written permission from Smith & Nephew, nor shall anyone make any use of it that is contrary to the expressed or implied wishes of Smith & Nephew.

Study Protocol—Device	
Safety and Performance of Q-Fix™ All-Suture Anchor System	Number: 17-5010-11
	Version: 2.0 05SEP2019
	Page: Page 31 of 62

relationship to study device and outcome. Incidences and number of subjects reporting device deficiencies will also be summarized. Further summaries of safety data may be described in the SAP.

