14. ADVERSE EVENTS AND DEVICE DEFICIENCIES

Adverse Events (AE) related to the study implant, or procedure including Adverse Device Effects (ADE), Serious Adverse Device Effects (SADE), Unanticipated Serious Adverse Device Effect (USADE), and Device Deficiencies (DevD) occurring from the time of the surgery until revision or study completion must be recorded on the appropriate CRF and reported. If the event is known to have been previously reported to Smith & Nephew, this must be noted on the CRF. After consent, in addition to all events related to the implant or the procedure, all serious adverse events (SAE), regardless of causality, must be recorded on the appropriate CRF and reported to the Sponsor and IRB if necessary. Events leading to a revision should be reported at all times regardless of causality.

Adverse Device Effects (ADE) occurring after study completion will be handled as product complaints reportable by the Sponsor and will not be entered into the study database.

CONFIDENTIAL AND PROPRIETARY

This document contains information that is confidential and proprietary to Smith & Nephew PLC and Smith & Nephew, Inc. and is intended for use only by Smith & Nephew and its manufacturer. It shall not be reproduced or copied in whole or in part, nor shall the contents be disclosed by any means without prior written permission from Smith & Nephew, nor shall anyone make any use of it that is contrary to the expressed or implied wishes of Smith & Nephew.

Study Protocol—Device	
Safety and Performance of Q-Fix™ All-Suture Anchor System	Number: 17-5010-11
	Version: 2.0 05SEP2019
	Page: Page 32 of 62

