14.1.6 Device Deficiency

A Device Deficiency (DevD) is an inadequacy of a medical device with respect to its identity, quality, durability, reliability, safety or performance. DevD includes malfunctions, use errors and inadequate labelling.

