14.2 REPORTING PROCEDURES

AEs of any kind and DevDs will be recorded in the applicable CRF and source notes. The Investigator will evaluate all AEs for relationship to the device and procedure, if applicable, seriousness, and severity.

CONFIDENTIAL AND PROPRIETARY

This document contains information that is confidential and proprietary to Smith & Nephew PLC and Smith & Nephew, Inc. and is intended for use only by Smith & Nephew and its manufacturer. It shall not be reproduced or copied in whole or in part, nor shall the contents be disclosed by any means without prior written permission from Smith & Nephew, nor shall anyone make any use of it that is contrary to the expressed or implied wishes of Smith & Nephew.

Study Protocol—Device	
Safety and Performance of Q-Fix™ All-Suture Anchor System	Number: 17-5010-11
	Version: 2.0 05SEP2019
	Page: Page 35 of 62

ADEs, SAEs, and DevDs will be submitted/entered into the CRF and reported to the Sponsor within 24 hours of the Investigator being informed about the event (Figure 14.2-1). For ADEs and DevDs, details of the product/procedure related to the event will be included and where applicable, pictures taken of the device. The deficient product should be retained for return to the sponsor unless it is contaminated (e.g. used dressings must not be retained). Updates to submitted information will be recorded in the CRF within 24 hours of the information being available to the Investigator.

[figure not shown]
All SAEs and ADEs will be reviewed by a medically qualified person appointed by the Sponsor to determine which, if any, meet criteria for expedited reporting to the regulatory authorities. The Investigator will inform the IRB of AEs according to the IRB requirements.

Depending on the nature of the AE, the Sponsor may request copies of the subject’s medical records, imaging, operative notes, as well as results of any relevant laboratory tests performed or other documentation related to the AE. If the subject was hospitalized, a copy of the discharge summary may be requested by the Sponsor and should be forwarded as soon as it becomes available. In certain cases, the Sponsor also may request a letter from the Investigator that summarizes the events related to the case.

CONFIDENTIAL AND PROPRIETARY

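### Protocol 8.2 presumes correct delivery whenever the operative report is silent, so a delivery fault known only from another record could be left out of the device-deficiency count

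*Protocol*

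**What the plan says.** Protocol 8.2 sets a default for the whole protocol: "unless otherwise noted in the operative report, the delivery system for the device worked correctly since the device was deployed". The default has one ground (deployment) and one stated exception (a note in the operative report).

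Other sections bear on it:

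- **Eligibility, Protocol 9.2, criterion 1:** "Subject has undergone arthroscopic or open soft tissue repair with Q-Fix™ All-Suture Anchor System". The safety population in 12.2 rests on the same condition.
- **Definition, Protocol 14.1.6:** "DevD includes malfunctions, use errors and inadequate labelling". A delivery malfunction is therefore a device deficiency.
- **Recording, Protocol 14.2:** "AEs of any kind and DevDs will be recorded in the applicable CRF and source notes". Section 14 starts the recording period at surgery and adds: "If the event is known to have been previously reported to Smith & Nephew, this must be noted on the CRF". Appendix 23.2, item 8a, makes the investigator record every observed device deficiency.
- **Output, Protocol 12.4:** "Incidences and number of subjects reporting device deficiencies will also be summarized".
- **Missing data, SAP 7.3:** no imputation is planned and only observed data are analysed. Protocol 11.1.2 adds: "Given the retrospective study design, data will be collected to the extent it is available".

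**The concern.** The default turns an absence of information in one document into a positive finding about the device, and the ground given for it cannot separate good delivery from bad. Eligibility is judged per subject, so criterion 1 implies at least one deployed anchor in nearly every enrolled subject. It does not imply that every anchor opened was deployed. A subject with one misfired anchor and one good replacement qualifies, and for the failed anchor the stated reason is untrue.

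The second difficulty is the single exception. The case history review covers operative, post-operative and discharge records, and section 14 expects some events to be known from earlier reports to the sponsor. Section 8.2 does not mention these sources. If abstractors apply it as written, a fault found in one of them is presumed not to have happened.

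What is at stake is a safety output. The only objective is the safety and performance of the anchor system, and 8.1.2 describes the anchor as pre-loaded in a disposable insertion tool. A delivery fault corrected during the operation need not lead to re-intervention, so the primary endpoint may never register it. The device-deficiency summary is where it should appear.

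**Working it through.** **1. Is there a figure to reproduce?** No. Neither document states a delivery-success rate, a device-deficiency rate or the completeness of operative reports. The check is mainly a comparison of texts.

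**2. Texts side by side.** Take a delivery fault that is absent from the operative report but present in another record.

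| Provision | Treatment of that fault |
|---|---|
| Protocol 8.2 | Presumed correct function |
| Protocol 14.1.6 | A malfunction or use error is a device deficiency |
| Protocol 14, 14.2 and Appendix 23.2 item 8a | Recorded; sources not limited to the operative report |
| SAP 7.3 | Only what was observed is analysed; nothing is filled in |

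The documents do not say which provision prevails. SAP 7.9.4 does not settle it: its text covers adverse-event tables and listings and does not mention device deficiencies. The table shells are not among the documents.

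**3. What 8.2 itself can change.** Let r be the true share of subjects with a delivery fault. Split the faults into a share a noted in the operative report, a share b noted only in another record, and a share c = 1 − a − b written nowhere.

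- Expected count if 8.2 is applied literally: n × r × a
- Expected count if section 14 is applied: n × r × (a + b)
- Effect of 8.2: n × r × b
- Chance of recording no fault, with subjects independent: (1 − r × a)^n against (1 − r × (a + b))^n

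The share c appears in neither count, so deleting the sentence cannot recover those faults.

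**4. Illustration on assumed inputs.** Take r = 1.6%, the failure figure in Protocol 13. It is only a stand-in, because the cited study concerns pullout during surgery, which is not the same as a delivery-tool fault. The values of a and b are pure assumptions. With n = 90 there are 90 × 0.016 = 1.44 expected faults.

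| a | b | c | Count, 8.2 literal | Count, section 14 | Chance of none, 8.2 literal | Chance of none, section 14 |
|---|---|---|---|---|---|---|
| 100% | 0 | 0 | 1.44 | 1.44 | 23.4% | 23.4% |
| 50% | 0 | 50% | 0.72 | 0.72 | 48.5% | 48.5% |
| 50% | 25% | 25% | 0.72 | 1.08 | 48.5% | 33.7% |
| 50% | 50% | 0 | 0.72 | 1.44 | 48.5% | 23.4% |
| 25% | 75% | 0 | 0.36 | 1.44 | 69.7% | 23.4% |

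Example for the third row: (1 − 0.016 × 0.50)^90 = 0.485 and (1 − 0.016 × 0.75)^90 = 0.337. At the maximum enrolment of 450, the same row gives 450 × 0.016 × 0.50 = 3.6 against 450 × 0.016 × 0.75 = 5.4. With the synopsis figure of 1.8% in place of 1.6%, the third row at n = 90 has a chance of none of 44.3% against 29.4%.

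The first two rows show no effect of 8.2. The second shows a real shortfall that comes wholly from incomplete charting.

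**5. Reading a zero.** If no deficiency were recorded, an exact 95% interval would have an upper limit of 4.0% for 0/90 and 0.8% for 0/450. Neither limit allows for faults that went unrecorded.

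**The case against.** The strongest reply is that 8.2 has no analytical consequence. No delivery-success variable, endpoint, derivation or table appears in either document. The endpoints are re-intervention, pain, range of motion and adverse events. Section 14 has its own recording duties from the time of surgery, and 8.2 does not expressly cancel them. SAP 7.3 forbids filling in missing values. A fault written nowhere is lost in any chart review, and the protocol openly says that it collects only what is available.

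Most of this stands, and it limits the point. Two stronger readings are tempting, and the documents do not support either:

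- **Silent operative reports are scored as delivery successes.** No such score or rate is planned, so there is no estimate of delivery performance to inflate.
- **Device deficiencies are understated.** This is possible but not shown. It requires faults that are documented outside the operative report and then dropped because of 8.2. Comparing half with full documentation (48.5% against 23.4% for no recorded fault) measures incomplete charting. It equals the effect of 8.2 only if every fault missing from the operative report is written in another record.

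What the reply does not remove is the conflict. Section 8.2 is written as a rule for the whole protocol, it names one source that can rebut it, and nothing says that section 14 overrides it. The caveat on available data does not help either: it leaves a gap as a gap, while 8.2 fills it favourably.

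**Conclusion.** The point holds as an internal conflict with a possible, one-directional effect. Applied literally, 8.2 classes a delivery fault known from another record as correct function, contrary to Protocol 14, 14.1.6 and 14.2 and to SAP 7.3. Any resulting error lowers the device-deficiency count. The presumption also gives no basis for a performance statement, because deployment is nearly guaranteed by eligibility and says nothing about a failed anchor that was replaced.

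The size cannot be determined from the documents. It equals n × r × b, and neither r nor b is given. In the illustration the effect at 90 subjects runs from 0 to 1.44 − 0.36 = 1.08 expected cases. The primary and secondary success rates do not change, since they depend on re-intervention, pain and range of motion. It should be corrected because a safety output is exposed and the remedy is cheap, not because a large bias has been demonstrated.

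**What to change.** 1. Delete the presumption from Protocol 8.2. State that a delivery fault found in any available record, including an earlier report to the sponsor, is recorded as a device deficiency under section 14.
2. Report the Protocol 12.4 summary as *documented device deficiencies (lower bound)*, carry that label into the SAP and its table shells, and draw no conclusion from deployment alone that delivery worked.
3. Where the CRF allows it without reopening completed charts, also show the number of subjects whose record does not describe delivery.

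Steps 1 and 2 are wording changes and need no new category of data. The downside is a slightly less favourable statement on delivery performance. Step 3 is conditional for a reason: Protocol 23.3 reports 106 + 99 + 24 = 229 subjects already enrolled at the amendment, and going back through their charts to classify delivery would not clearly be cheap. None of these steps recovers faults that were never written down; the lower-bound label is there to say so.
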